RESEARCH PROTOCOL

NCT03279458

Title	Non-invasive tidal volume monitoring using the Linshom Respiratory Monitoring Device
Faculty Sponsor	[name]
Principle Investigator/Co-investigators	[name] [name] [name]
Abstract	
Many post-operative complications arise from patients who breathe inadequately. Inadequate respiration, whether the result of surgery or the anesthesia, causes a decrease in blood oxygen saturation and an increase in carbon dioxide partial pressure. Both of these surrogate measurements of respiration may pose a challenge to measure. Some administer exogenous oxygen to all patients as they leave the operating room in order to maintain the blood oxygen saturation. This renders the oximeter a less sensitive metric of depressed respiration. In the face of decreased respiration, the carbon dioxide levels continue to increase slowly and often go undetected unless blood gases are measured. Indeed carbon dioxide blood levels are the only metric to detect inadequate ventilation using this surrogate index.
 
Monitoring ventilation is a serious challenge outside of critical care settings. In fact, there are no monitors available that can measure tidal volume or relative tidal volume outside of these settings.
 
Linshom is a novel instrument that tracks relative respiration by measuring the excursions of the temperature swings between inspiration and expiration and normalizing them to the patient's breathing. This monitor may be the first non-invasive monitor to measure relative tidal volume in non-critical care settings.

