
Background
	
Oxygenation – the process of delivering oxygen to the lungs – is often much simpler to achieve than ventilation, since only a small volume of oxygen must be delivered to oxygenate the patient and provide a reserve. Carbon dioxide, however, constantly accumulates and depends on ongoing ventilation to eliminate it from the lungs.
 
Direct automatic ventilation monitors tend to be cumbersome. They typically require chest straps or EKG-type stickers to be placed on the patient’s chest. EKG signals themselves can be used to detect inhalation and exhalation, but the noise of EKG monitors tends to make this method unreliable. In most cases, the patient needs to be lying quite still in order for accurate ventilation monitoring and even then they measure respiratory rate and not tidal volume.
 
The gold standard method to measure the adequacy of ventilation is to measure the exhaled carbon dioxide concentration. Exhaled gas almost always contains carbon dioxide that may be measured using either sidestream or mainstream capnography. However, the carbon dioxide tension is only a surrogate measure of ventilation since it is the changes in tidal volume per breath or minute ventilation that determines the adequacy of respiration and therefore the carbon dioxide tension. Capnography accurately measures the respiratory rate and the net effect of ventilation without reporting the tidal volume. Knowing the tidal volume before the carbon dioxide tension begins to increase provides an opportunity to intervene before the clinical situation has deteriorated too much. Linshom is a reliable, effective patient ventilation monitor that is minimally invasive, simple, inexpensive, fast responding and tracks relative tidal volume outside of critical care settings.

Purpose
	
To determine whether a non-invasive, temperature-based respiratory instrument could track tidal volume (V_t) in patients.

Specific Aim(s)
	
The primary purpose of this investigation is to evaluate whether a non-invasive, thermodynamic temperature-based instrument, Linshom, can accurately and consistently track tidal volume as measured by closed loop mechanical ventilator.

Study Period (inclusive years)
	
The study will be completed over a period of one week.

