
Study Design
	
Flyers advertising the study will be placed around campus on designated bulletin boards. Individuals interested in the study will be able to call the number (PI Office Number: [name]). If the individual meets the study criteria, then he or she will be scheduled for a study session, which will take place in room N200-13 of the respiratory therapy department. After completing the visit, the volunteer will receive a \$10.00 gift card.
 
The Linshom detector, which is comprised of two rapid responding medical-grade thermistors in close proximity to the mouth/nose (sensor) and a thermistor remote to the airway, will be mounted in the CPAP facemask to measure the temperature during breathing. The CPAP will be connected to a Servo-I ventilator (Maquet) with a circuit and disposable filter. The volunteers will be instructed to breathe normal through the CPAP mask on room air. The excursions of the thermistor tracings (from valley to peak) will be recorded by the Linshom device and displayed continuously on a laptop monitor in a waveform. The tidal volume will also be measured by the ventilator and the data downloaded in a Compact Flash card. The temperature profiles from the sensors and the relative tidal volume will be correlated with the tidal volumes measured by the ventilator.

Inclusion Criteria
	
Healthy volunteers 18 years of age or older will be recruited from the Medical School at the University of Mississippi.

Exclusion Criteria
	
Individuals who are pregnant, suffer from claustrophobia, or who have had a recent respiratory or gastrointestinal illness will be excluded. Volunteers deemed not to have the capacity to provide informed consent will not be enrolled.

Number of Subjects (anticipated)
	
40.

Outcome Measures
	
Every volunteer recruited in this study will be monitored by the study investigators during data collection. Linshom readings showing the temperature changes and tidal volume measured by ventilator will be collected.

Study Endpoints
	
The subjects will breathe through the mask for about 5 minutes, and will be observed during this time by the study investigators. Continuous data for tidal volume and temperature will be collected during this time and the data will be analyzed post-hoc.

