Private Health Information	No medical record information will be collected – no other volunteer information will be recorded. Volunteer numbers will be paired with study numbers in a single Microsoft Excel spreadsheet. All study information will thereafter refer to study numbers.
Statistical Methodology	We shall correlate the tidal volumes measured with the Linshom detector with the respective tidal volumes from the mechanical ventilator. A least squares regression analysis (with the coefficient of determination r-squared) and a Bland Altman plot will be prepared. P<0.05 will be accepted.

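### The plan names no unit of analysis and makes no allowance for repeated breaths; if breaths are pooled across volunteers, the P value can be badly miscalibrated and r-squared can misstate tracking

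*Combined protocol and SAP*

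**What the plan says.** The Specific Aim(s) section asks whether the device "can accurately and consistently track tidal volume as measured by closed loop mechanical ventilator".

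On data, Study Endpoints says "The subjects will breathe through the mask for about 5 minutes" and "Continuous data for tidal volume and temperature will be collected during this time and the data will be analyzed post-hoc". The anticipated number of subjects is 40. Study Design adds "The volunteers will be instructed to breathe normal through the CPAP mask on room air", so no change in tidal volume is planned.

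On scale, the Abstract says that the device "tracks relative respiration by measuring the excursions of the temperature swings between inspiration and expiration and normalizing them to" the breathing of that patient, but no section gives the normalisation rule. Study Design says "The temperature profiles from the sensors and the relative tidal volume will be correlated with the tidal volumes measured by the ventilator". No normalisation of the ventilator values is stated.

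On analysis, Statistical Methodology consists of "We shall correlate the tidal volumes measured with the Linshom detector with the respective tidal volumes from the mechanical ventilator", followed by "A least squares regression analysis (with the coefficient of determination r-squared) and a Bland Altman plot will be prepared. P<0.05 will be accepted". It names no unit of analysis, no volunteer term, no allowance for repeated readings and no rule for combining volunteers.

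**The concern.** Tracking is a question about change within a person. Consistency is whether that tracking holds from one person to the next. Ordinary least squares on paired readings answers neither unless the plan says how the breaths of one volunteer are handled.

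The text fits three readings:

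- **All breaths in one regression.** Breaths from one person are treated as independent, so the P value can be wrong. The r-squared mixes differences between people with tracking within people. Because volunteers breathe normally, within-person variation may be small beside between-person variation.
- **One mean per volunteer.** The P value is not distorted by repeated breaths, but the result describes differences between people and does not test tracking.
- **One regression per volunteer.** This addresses tracking, and the 40 results would show consistency. The plan does not commit to it and gives no rule for summarising the results.

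This regression and the Bland-Altman plot are the only analyses stated for the aim. If the first reading is taken, the reported P and r-squared could mislead on whether the device tracks tidal volume.

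**Working it through.** **Inputs from the protocol.** 40 volunteers; about 5 minutes each; P<0.05 (taken as two-sided). There is no sample-size calculation to reproduce.

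**Assumed inputs (the protocol gives none).** 8–20 breaths per minute; intraclass correlation (ICC, the share of variance that lies between people) 0.2–0.7 for each signal, up to 0.8 for the ventilator in some own-mean settings; breath-to-breath autocorrelation 0–0.5. For r-squared: between-person log-SD 0.25, within-person CV 10–25%, non-tracker device CV 15%, 75 breaths, autocorrelation 0.3.

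**Number of readings.** 8 × 5 = 40 to 20 × 5 = 100 breaths per person, so 40 × 40 = 1,600 to 40 × 100 = 4,000 in all.

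**False positives, both signals un-normalised, closed form without autocorrelation.** The variance of the pooled slope is inflated by DEFF = 1 + (n − 1) × ICC_x × ICC_y. The actual error rate is 2 × [1 − Φ(1.96/√DEFF)].

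- ICC 0.2 and 0.2, n = 40: DEFF = 1 + 39 × 0.04 = 2.56; error 22.1%.
- ICC 0.5 and 0.5, n = 75: DEFF = 1 + 74 × 0.25 = 19.5; error 65.7%.
- ICC 0.7 and 0.7, n = 100: DEFF = 1 + 99 × 0.49 = 49.51; error 78.1%.

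Simulation at the same three settings gave 22.0%, 65.3% and 78.9%.

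**False positives by normalisation, simulated, device unrelated to ventilator volume.**

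| Scales compared on pooled breaths | P<0.05 |
|---|---|
| Both signals differ between people | about 22–79% |
| Only one signal differs between people | about 5% without autocorrelation; 16–22% at 0.5 |
| Device normalised to its first breaths (first 5 taken), against mL | about 35–63% |
| Device normalised to each person's own mean, against mL | about 0–6% |
| Both signals normalised per person | about 5% without autocorrelation; 13–15% at 0.5 |

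These are ranges over the settings tried, not bounds.

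**The other two readings.** One mean per volunteer gave 4.4–5.7%. With separate regressions, a single volunteer's P was below 0.05 in about 5% without autocorrelation (0.05 × 40 = 2 volunteers by chance) and about 12% at 0.5 (0.12 × 40 ≈ 5 volunteers). A one-sample t test on the 40 within-volunteer slopes stayed at about 4–6% in every scenario.

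**Pooled r-squared.** With log-SD 0.25, ICC ≈ 0.0625/(0.0625 + CV²), which is 0.862, 0.735 and 0.500 at CV 10, 15 and 25%.

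- *Dilution.* A perfect tracker, normalised to its own mean and plotted against mL, gives about 1 − ICC = 0.138, 0.265, 0.500 (simulated 0.141, 0.264, 0.477). Its within-person r-squared is 1.0.
- *Inflation.* A device that carries each person's mean volume in mL but follows no breath gives about ICC_ventilator × ICC_device, with ICC_device = 0.735 at CV 15%: 0.634, 0.541, 0.368 (simulated 0.613, 0.521, 0.360). Its within-person r-squared is about 0.02.
- *Exception.* If both signals are normalised per person, pooled and within-person r-squared coincide (0.90 for each when the true within-person correlation is 0.95).

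**Consistency.** With both signals relative, ventilator CV 15% and device noise CV 10%, the SD of the 40 slopes is 0.09 if all volunteers are tracked, 0.45 if 10 are not and 0.51 if 20 are not. The SD of slopes therefore reveals failures that a test of the mean slope does not.

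**The case against.** The strongest reply is that the protocol nowhere says breaths will be pooled. Referring to respective volumes means only that the readings are paired. Separate regressions per volunteer fit the text equally well and would show consistency directly, lacking only a summary rule. This stands, and it is why the point is conditional.

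Second, every ICC, autocorrelation and breathing rate is assumed, and the false-positive rate runs from near 0% to 79%. This also stands: the figures show how much the unstated choices matter and do not predict this trial's error rate. In some pooled cases the rate is close to 5%, so a reader who infers that pooling always makes P too small would be wrong.

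Third, the false-positive rates describe a device with no information at all. The plan has no rule equating P<0.05 with tracking, and the Bland-Altman plot does not depend on that P value. This limits the consequence. The plot does not close the gap, though: no rule puts a relative device reading and a volume in mL on one scale, and any limits of agreement face the same repeated-breath problem.

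A reader might also infer from the two r-squared ranges that a device tracking every breath could score below one tracking none. The ranges do not support that, because they come from different scales. With one scale held fixed and the same inputs, the tracker scores higher each time:

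- own-mean device against mL: 0.14–0.48 for the tracker, below 0.001 for the non-tracker;
- both in mL: 1.00 against 0.36–0.61;
- both relative: 1.00 against below 0.001.

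A reversal on un-normalised data can be constructed only by also giving the two devices very different between-person relations (correlation 0.9 for the non-tracker, none for the tracker). Nothing in the protocol suggests this.

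**Conclusion.** The concern holds in conditional form. The plan leaves the unit of analysis and the handling of repeated breaths open. If its least-squares method is applied to pooled breaths, P can be far too liberal or too conservative, depending on a normalisation the protocol mentions but does not define. Pooled r-squared can be inflated or diluted by between-person differences unless both signals are normalised per person. The sizes rest wholly on the assumed inputs.

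The protocol does not support saying that the sponsor will pool, that P is necessarily too small, that a tracker would rank below a non-tracker, or that the study session is compromised. The breath-level data will exist, so a sound analysis remains available. This is a cheap improvement, worth making because it concerns the only regression planned for the aim.

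**What to change.** In Statistical Methodology, make the volunteer the unit of inference:

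1. State the normalisation rule for the device, and say whether the ventilator values are normalised too.
2. Fit a within-volunteer regression for each of the 40. Report the mean within-person slope with a t-based 95% CI across volunteers, the between-volunteer SD of slopes (the measure of consistency) and a within-subject correlation.
3. Draw no conclusion from a P value or r-squared computed on pooled breaths.
4. Put both methods on the same scale in the Bland-Altman plot. If intervals are given for its limits, base them on volunteers.

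A mixed model with random slopes is optional, since the t test on slopes already held its error rate.

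The cost is a few sentences of wording, slightly more analysis work and possibly wider intervals. No new data are needed and the study session does not change.

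### The aim is accurate tracking, but the only threshold is P<0.05, which speaks at most to association; no bias, limits of agreement or slope is set in advance as adequate

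*Combined protocol and SAP*

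**What the plan says.** Specific Aim(s) sets the question: whether the device "can accurately and consistently track tidal volume as measured by closed loop mechanical ventilator".

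Statistical Methodology, in full, plans three outputs and gives one threshold:

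- The opening sentence covers the correlation only: "We shall correlate the tidal volumes measured with the Linshom detector with the respective tidal volumes from the mechanical ventilator".
- The next adds a fitted line and an agreement display: "A least squares regression analysis (with the coefficient of determination r-squared) and a Bland Altman plot will be prepared".
- The section then closes with the single threshold: "P<0.05 will be accepted".

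The null hypothesis, the sidedness of the test and the unit of analysis (breath, volunteer mean or other) are not stated. Outcome Measures and Study Endpoints describe what is recorded and give no criterion for success. No section states an acceptable bias, limits of agreement, slope or r-squared.

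On the conditions, Study Design says "The volunteers will be instructed to breathe normal through the CPAP mask on room air", and Study Endpoints says "The subjects will breathe through the mask for about 5 minutes".

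On the scale, the Abstract describes temperature swings that are scaled to each person's own breathing, so the reading is relative, and Study Design says "The temperature profiles from the sensors and the relative tidal volume will be correlated with the tidal volumes measured by the ventilator". No baseline period for the normalization is defined.

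**The concern.** Accuracy concerns how far the two readings differ, and consistency concerns whether that holds from breath to breath and from volunteer to volunteer. A P value against zero association answers neither: rejecting it shows only that the two readings are related to some degree. Applying P<0.05 to a mean bias of zero would not help, because a non-significant result does not demonstrate agreement.

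The planned outputs are the right kind, but there is nothing to read them against. With no limit fixed beforehand, any width of the Bland-Altman limits or any slope can be called adequate after the data are seen. A difference between methods also needs one scale, and a relative reading cannot be subtracted from a volume until a baseline is defined.

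This matters more because volunteers breathe normally. When tidal volume varies little, a device that always reads 100% of baseline looks fairly accurate while tracking nothing. A significant P value does not show that Linshom improves on that.

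**Working it through.** **Inputs from the documents.** 40 volunteers, about 5 minutes each, threshold 0.05. The figure of 40 has no derivation to reproduce.

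**Assumed inputs, not in the documents.** Two-sided test of zero association; breath-level pairing; 12 to 20 breaths/min, so 60 to 100 breaths per volunteer and 2400 to 4000 in all; tidal-volume CV 15% to 20%; zero mean bias; breath-to-breath autocorrelation 0 to 0.8; between-volunteer SD of slope 0.1 to 0.3.

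**Step 1. Correlation needed for P<0.05:** r = t/√(n − 2 + t²).

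- One pair per volunteer, n = 40: t = 2.024, r = 2.024/√(38 + 4.10) = 0.312, r-squared 0.097.
- Breaths pooled as if independent: n = 2400 gives 0.040; n = 4000 gives 0.031.

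**Step 2. How often a weak device reaches P<0.05.**

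- *One pair per volunteer (n = 40, simulated):* 24% at r 0.2, 48% at r 0.3, 92% at r 0.5.
- *Repeated breaths, one-sample t-test on 40 within-volunteer slopes:* simulated over eight combinations of breaths (60 or 100), slope SD (0.1 or 0.3) and autocorrelation (0 or 0.8), 4,000 trials each. Results: about 5% at mean r 0, 35% to 99% at 0.1, 87% to 100% at 0.2, 99.8% to 100% at 0.3.

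Hand check of the least favourable case at r 0.2 (60 breaths, autocorrelation 0.8, slope SD 0.3):

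- Effective breaths: 60 × (1 − 0.64)/(1 + 0.64) = 13.2.
- Sampling variance of one slope: (1 − 0.04)/13.2 = 0.073.
- Standard error of the mean slope: √((0.09 + 0.073)/40) = 0.064.
- Ratio 0.2/0.064 = 3.1 against a critical value of 2.02, so power is about 87%.

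I quote roughly 85% to 100% to allow for simulation error.

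**Step 3. Limits of agreement (half-width, percent of baseline) at r 0.2, CV 15% / 20%.**

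| Device | Formula | Half-width |
|---|---|---|
| Always reads 100% of baseline | 1.96 × CV | 29.4 / 39.2 |
| Same CV as the ventilator readings | 1.96 × CV × √(2(1 − r)) | 37.2 / 49.6 |
| Regression-calibrated | 1.96 × CV × √(1 − r²) | 28.8 / 38.4 |

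The equal-CV device is worse than the constant reading by a factor of √1.6 = 1.26. The calibrated device is marginally better, but its slope on ventilator volume is r² = 0.04, so it responds to about 4% of a change.

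**Step 4. Correlation at which a device matches the constant reading.**

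- Equal CVs: √(2(1 − r)) = 1, so r = 0.50.
- Unit slope with additive error: √(1/r² − 1) = 1, so r = 0.71.
- Calibrated: any r above 0 does better.

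**The case against.** Four objections deserve weight.

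- **P<0.05 may be no more than the conventional significance level.** A reader might infer that the plan declares the device accurate once P<0.05. The documents do not say so; no section ties the aim to a P value. This stands, but it leaves the plan with no criterion at all for its stated aim.
- **The plan would expose a poor device.** A reader might infer that weak tracking would go unseen. That is not supported. At r 0.2 to 0.3 the planned r-squared would be 0.04 to 0.09, the regression would give a slope, and the Bland-Altman plot would show wide limits. What is missing is the yardstick, not the information.
- **The high pass rates rest on an analysis the plan does not state.** The t-test on 40 slopes is an assumption. Continuous recording makes breath-level pairing likely, but it is not specified. With one pair per volunteer, a device at r 0.2 reaches P<0.05 in only 24% of trials.
- **The comparison with a constant reading is model-dependent, and the comparator is not in the protocol.** This also stands. It is offered as a natural benchmark for quiet breathing, not as a property of Linshom.

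A reader might also picture a device that correlates almost perfectly while reading half the true volume. That example does not carry over, because normalizing to the patient's own breathing would cancel a fixed proportional error.

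**Conclusion.** The point holds, and should be fixed. The documents set no standard for bias, limits of agreement or slope; their one threshold concerns association at most; and the common scale that any agreement limit needs is undefined. These conclusions come from the text and do not depend on the simulations.

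The size is illustrative. P<0.05 needs a correlation anywhere from 0.312 down to about 0.03, depending on a unit of analysis that the plan leaves open. On the assumed within-volunteer analysis, a device at mean r 0.2 would nearly always be significant, yet under the equal-CV model it would agree less well than a constant reading. Under the calibrated model it would agree very slightly better while hardly responding to change. The documents do not support saying that Linshom performs this way, that P<0.05 is the declared success rule, or that the planned outputs are uninformative.

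**What to change.** Before data collection, amend Statistical Methodology as follows.

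1. State that P<0.05 for a correlation or slope is descriptive and is not evidence of accuracy.
2. Make Bland-Altman bias and limits of agreement the primary analysis, using a method that allows for repeated breaths within volunteer, with 95% confidence intervals. Express both methods as percent of baseline, define the baseline period in advance, and leave its breaths out of the comparison.
3. Report the mean within-volunteer slope of Linshom on ventilator tidal volume with its confidence interval, and its between-volunteer SD.
4. Conclude that tracking is accurate and consistent only if both conditions hold:
   - the confidence intervals of both limits lie inside a margin that the sponsor fixes and justifies beforehand;
   - the device has a smaller root-mean-square error than a constant reading of 100% of baseline, or meets a slope criterion set in advance.
5. If no margin is set, report the estimates with confidence intervals and make no accuracy claim.

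The second condition in item 4 must be binding. In simulation (CV 15%, 40 volunteers with 75 breaths each, between-volunteer bias SD 3%, all assumed), a constant reading meets a 35% margin in every trial. That margin only illustrates the problem; none is proposed here.

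The cost is statistical wording, one margin, one baseline definition and the loss of the baseline breaths from the comparison. No extra volunteers or recordings are needed. The downside is that a weakly tracking device can now fail, and the verdict depends on the margin chosen, so its justification should be written down.
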